# CLARKSON UNIVERSITY HUMAN SUBJECTS RESEARCH INSTITUTIONAL REVIEW BOARD PROPOSAL

## 1. Research Summary (400 words or less)

People with hypermobile Ehlers-Danlos Syndrome/Hypermobility Spectrum Disorder (hEDS/HSD) often have pain, coordination problems, and low tolerance to activity and exercise. Therapeutic exercise is considered one of the most effective treatment options in the improvement of pain and disability in people with hEDS/HSD.(Engelbert et al, 2017; Simmonds et al, 2017) The Pilates Method of exercise has 6 guiding principles: centering, concentration, control, precision, flow and breathing. Pilates is a series of exercises that promote core stability, muscle strength and flexibility and attention to muscle control, posture and breathing (Wells et al, 2012). Pilates was developed for dancers who are often hypermobile, and has been recommended for people with hEDS/HSD.(McNeill, 2018) A recent systematic review concluded that Pilates is beneficial for decreasing pain and disability in a number of conditions.(Byrnes, 2018) Although a large survey of 946 people with hEDS/HSD found that 26% of respondents considered Pilates a helpful form of exercise,(Simmonds, 2017) there appears to be no research into the effectiveness of Pilates for this population.

One of the co-PI ([name]) is a professional Pilates instructor who has created an internet-based Pilates course designed specifically for people with hypermobility. This course guides participants through developing body awareness and control through slow and deliberate movements. Eighty people have subscribed to this course since it was first offered in August 2016. When people purchase access to these internet modules, [name] is able to track how often they access the modules; hence, we would have a measure of compliance with the program.

The current research project proposes to measure pain, function, and common symptoms in individuals before and after 8 weeks of using this on-line Pilates module, and will follow up 6 months later. Before starting Pilates, subjects will complete a series of on-line questionnaires using Survey Monkey, then will progress independently through the 5 video modules, performing the exercises 3 times/week. We will track utilization of the modules on-line as a measure of compliance. At the end of the 8 weeks, we will reassess pain, function and symptoms, and we will contact subjects to collect similar data again 6 months after completing the intervention.

### 2. Introduction

Hypermobile Ehlers-Danlos Syndrome (hEDS) and Hypermobility Spectrum Disorder (HSD) are conditions characterized by abnormal collagen, resulting in many tissues in the body being overly flexible. Joint hypermobility is most obvious, hence the former name for this condition: joint hypermobility syndrome. HSD and hEDS comprise a continuum in which diagnostic criteria for hEDS are narrower. However, the pain and other symptoms such as sleep disturbance, fatigue, anxiety, proprioceptive (body position awareness) deficits, autonomic nervous system dysfunction, GI distress, can exist equally for both conditions.(Tinkle, 2017) The current study seeks to involve people throughout the continuum, hence hEDS/HSD.

Individuals with hEDS/HSD often have movement disorders, such as balance issues, due in part to reduced proprioception (Smith 2013), fear of movement or kinesiophobia and a reluctance to move due to the presence of chronic pain. Pain is often one of the first symptoms to appear with hypermobility (Smith 2013). Other issues such as fatigue and autonomic disorders such as Postural Orthostatic Tachycardia Syndrome (POTS) are also common in hEDS/HSD; these comorbidities can decrease desire to exercise as well as tolerance to upright (standing) exercise. Therapeutic exercise is considered one of the most effective treatment options in the improvement of pain and disability in hEDS/HSD, but optimal type, frequency and intensity are not known.(Smith, 2014; Engelbert, 2017) However, pain, fatigue and fear are common barriers to exercise among people with hEDS/HSD.(Simmonds, 2017) Mind-body exercises, such as Pilates, Tai Chi, and yoga have been recommended for people with hEDS/HSD based on the

fact that these mind-body activities are typically gentle and foster relaxation and improved body awareness.(McNeill, 2018; Russek, 2018)

Joseph Pilates (1883-1967) called his method 'Contrology' - a complete coordination of mind and body. It was only after his death, that the method grew in popularity and became known as the Pilates Method. The original 6 guiding principles of centering, concentration, control, precision, flow and breathing remain true today. The method comprises a series of exercises that promotes core stability, muscle strength and flexibility and attention to muscle control, posture and breathing (Wells et al, 2012). Pilates has become a mainstream, low-impact exercise with perceived benefits both physical (balance, flexibility, pain reduction, disability reduction) and psychological (mindfulness) (Pilates and Miller, 1998). It can be safely performed by all ages and abilities without the need for special equipment.

The Pilates Method of exercise has been widely used in physical training and rehabilitation (Latey, 2001, Kloubec 2011). Although a large survey of 946 people with hEDS/HSD found that 26% of respondents considered Pilates a helpful form of exercise, (Simmonds, 2017) there appears to be no research into the effectiveness of Pilates for this population. Used as a gentle, rehabilitation exercise method, Pilates could be a safe and effective type of exercise to manage the symptoms of pain, fatigue, disability and anxiety related to having hEDS/HSD. Furthermore, starting exercises supine (lying down) may be better tolerated by people with autonomic dysfunction, such as POTS, than exercises in the upright position.

A systematic review concluded that Pilates can be beneficial for decreasing pain and disability in a number of chronic conditions, including chronic low back pain, multiple sclerosis, and chronic neck pain. (Byrnes, 2018) However, there is no research involving people with hEDS/HSD. There are several mechanisms by which movement training such as Pilates can be beneficial for people with hEDS/HSD. One is improved muscle strength and tone, which can stabilize hypermobile joints. Another is through improved body awareness, which may improve coordination. Also, Pilates could encourage healthier breathing patterns and a calming response. Because of the proprioceptive deficits common in hypermobile individuals, use of small props like balls and bands can improve sensory awareness and help these individuals connect with their bodies.(Lauber, 2014)

Anxiety is a common symptom in people with hEDS/HSD.(Bulbena, 2017) Anxiety may be due to fear of movement associated with pain or proprioceptive deficits, or may be due to the racing heart rate associated with POTS. Kinesiophobia is an extreme fear of movement due to fear of vulnerability to pain or injury. Kinesiophobia appears to be common in hEDS/HSD, and may lead to decreased activity with resulting increased deconditioning and pain.(Celletti, 2013) Pilates has been shown to decrease kinesiophobia in patients with chronic low back pain,(Cruz-Diaz, 2018) and osteoporosis, but has not been studied in hEDS/HSD.(Oksuz, 2017)

People with hEDS/HSD appear to commonly hold their breath in an attempt to improve stability; increased tone/tension in accessory muscles of respiration (i.e., muscles other than the diaphragm, which is designed for continuous breathing) can cause pain and abnormal movement patterns. Pilates involves retaining breathing patterns, introducing simple mindfulness techniques and sensory awareness that can have an instant calming effect and reduce anxiety.(McNeill, 2017, Caldwell, 2013)

The current proposal is to study the potential benefits of an online Pilates course designed specifically for individuals with some form of hypermobility. The course was designed by a qualified Pilates teacher who also has hypermobility. Two of the PI ([name] and LR) have received very positive anecdotal feedback from people with hEDS/HSD who have taken this Pilates course. The course includes 5 modules of about 25 minutes each. Each module includes education about proper body positioning and movement, relaxation training, and Pilates exercises. The exercises are very gentle, and are often taught with modifications to make them

easier, if needed by the subject. Most are done lying down on the ground, some are done sitting in a chair, and a few are done standing. Common movement errors are explained and demonstrated to facilitate correct movement. Safety precautions (e.g., holding on to a chair back for balance during the standing exercises, if needed) are also clearly explained. In the 3 years that this course has been available to the public, the developer ([name]) has never received any feedback that the exercises caused any harm. Furthermore, a Cochrane Review of Pilates for chronic low back pain including 10 studies and 510 patients found minor or no adverse events in any of the research studies involving Pilates exercises.(Yamoto, 2015) Consequently, Pilates can be considered a very safe form of exercise.

Subjects will be asked to do their Pilates with the video at least 3 times/week, to go through the modules in order, and to complete all modules by the end of the 8th week. However, subjects may choose how often to repeat given modules, and may return to modules that they find particularly helpful. While allowing subjects this choice results in an intervention that is somewhat variable among subjects, we feel it gives subjects some ownership over their program and reproduces how the modules are used in practice.

We propose to use the following outcome measures:

- The Bristol Impact of Hypermobility (BloH) questionnaire to measure function, quality of life, and common symptoms of hEDS/HSD. (Palmer, 2017)
- The International Physical Activity Questionnaire Short Form (IPAQ), supplemented by additional questions about mind-body and strengthening exercise, to measure physical activity.(Booth, 2000)
- The Revised Body Awareness Rating Questionnaire (R-BARQ) to measure mind-body awareness and dysfunctional breathing patterns. (Dragesund, 2018)
- The Tampa Scale of Kinesiophobia, short form (TSK-11), to measure kinesiophobia, or fear with movement. (Woby, 2005)

Our primary outcome measures will be a hypermobility-specific functional/disability measure, The Bristol Impact of Hypermobility (BloH) questionnaire.(Palmer, 2017) The BloH is a 55 item questionnaire that asks about pain, fatigue, joint instability, function, self-efficacy and attitudes about having hypermobility. It is the only outcome measure specifically validated for hypermobility-related conditions, and it is recommended by the international Common Data Elements initiative, whose goal is to encourage EDS researchers to use consistent outcome measures.

We will also measure physical activity, to determine whether participation in Pilates allows people to become more active. The International Physical Activity Questionnaire Short Form is a validated survey assessing physical activity during work, sport, and leisure time. (Booth, 2000) We will add questions that will track participation in mind-body exercise, such as Pilates, yoga, Tai Chi, etc. and strengthening, as these activities are not included in the IPAQ.

Kinesiophobia will be assessed through the Tampa Scale of Kinesiophobia, short form (TSK-11), which is an 11-question survey asking about fear of movement and fear of injury. (Woby, 2005) The Tampa Scale of Kinesiophobia is one of the recommended Common Data Elements for EDS. We will also collect qualitative data from weekly electronic contact.

The Revised Body Awareness Rating Questionnaire (R-BARQ) includes 12 questions that ask about body awareness, response to discomfort, breathing patters, and physical response to stress.(Dragesund, 2018) This tool may provide insight into the mechanism by which functional improvements are achieved, by correlating functional improvements with improved body awareness, relaxation, effective breathing, etc.

We will also solicit qualitative feedback about the Pilates program through weekly emails. This qualitative information will build upon a recent study using qualitative methods to assess

attitudes towards exercise among people with hEDS/HSD.(Simmonds, 2017)

The current study will repeat the questionnaires at the end of the 8 week intervention, to assess change, and again 6 months later to determine whether any changes have been maintained. We will also monitor whether subjects continue to do the Pilates exercises at 6 months, either using the videos or on their own. If findings in the current study are encouraging, a more formal randomized control trial would be an appropriate progression. The qualitative data may provide useful information about how to implement a follow-up study more effectively.

# 3. Objectives and Hypotheses

- 1. Implement a pilot study to assess whether this on-line Pilates course for people with hEDS/HSD results in beneficial changes when compared to a wait-list comparison group. We understand that the evidence will not be strong with a non-random comparison group, but having a comparison group is better than not having one. We hypothesize that 8 weeks of this specialized Pilates training will result in:
  - a. Decreased pain and symptoms, improved function and quality of life (measured using the BloH),
  - b. Increased physical activity (measured using IPAQ with additional questions)
  - c. Improved body awareness (R-BARQ) and less dysfunctional breathing patterns (R-BARQ)
  - d. Decreased fear of movement (TSK-11).
- 2. Pilot test the proposed outcome measurement tools for such a future study. We are looking for basement and ceiling effects, as well as change over time.
- 3. Explore whether certain patterns of implementation of the on-line course are associated with better outcomes. For example, is it better to repeat one module multiple times before moving on, or to move around among modules? This will be descriptive correlational data.
- 4. Gather qualitative data to better understand factors that may influence compliance or maximal benefit. These data can inform future research into either Pilates or use of internet-accessible exercise training for this population. This qualitative information also provides insights into factors that influence participation in exercise within this population, and whether certain patterns are observed among people who benefit from the program compared to those who do not.

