## 6. Study Design and Methods

a. Procedure for data collection and intervention, including duration of subject involvement: The intervention is provided through an on-line Pilates module commercially available at https://[name]/strengthen-your-hypermobile-core/. "Strengthen Your Hypermobile Core" has 5 modules. Subjects will be asked to complete the modules in order, as the modules build upon one another. However, subjects may repeat any modules at any time, with the goal of completing all 5 modules within the 8 week period. This allows subjects the flexibility to customize their participation by using the modules they feel are most helpful. Users who typically access this Pilates course have this same flexibility so, while it adds variability to the intervention, it better reflects how the program is actually used.

Subjects will be asked to do their Pilates practice while watching the videos (not from memory) to ensure that they are performing techniques optimally. Each module lasts 25 minutes, but includes some resting activities so modules are not vigorous or fatiguing for most people. Nonetheless, subjects will be instructed to omit activities that they feel they cannot do safely. Subjects can pause a session to add more rest breaks, if needed, or stop and complete a session later. Subjects will commit to doing 3 Pilates modules per week, for a total of 75-90 minutes/week (depending on the exact length of the modules they do). The commercial application of this on-line Pilates course provides the ability to track access to each module, so we will have data regarding compliance and which modules are used at which time. Data about module utilization will be linked to the subject's self-created research code, which will keep this data anonymous as we cannot link the self-created research code to any identifiable individual.

Subjects will complete questionnaires before starting the on-line Pilates modules. Completing these questionnaires on SurveyMonkey is likely to take 30-45 minutes. These questionnaires are described in detail in section b, below.

Subjects will receive a weekly email, encouraging them to continue doing Pilates at least 3 times/week. This email will also ask them to complete some narrative questions on SurveyMonkey regarding whether they have had any problems completing the Pilates

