sessions and, if so, why. We will also ask if they have any comments about the modules or about their experience. We will also ask about any changes in pain, either related to the Pilates practice, or unrelated. The contact email will also remind them that they can contact one of the PI (JD) if they have questions or problems with the Pilates, or (LR) if they have any questions about research participation.

At the end of 8 weeks, subjects will be asked to repeat the initial questionnaires on SurveyMonkey, and comment on their experience doing the Pilates. This is likely to take about 60 minutes. Subjects will continue to have access to the Pilates modules and we will encourage them to continue using the modules. We will track whether individuals do access the modules over the next 6 months.

Six months after subjects complete the 8 week exercise session, we will contact each subject again and ask him/her to repeat the initial questionnaires on SurveyMonkey, and again comment on whether they felt the Pilates was helpful.

We will also include an 8-week wait-list group constructed from subjects asking to participate after we have already recruited 225 subjects. This wait list is primarily because we do not want to be so overwhelmed by participants that we cannot manage them effectively (responding to questions about the Pilates, sending out follow-up surveys, etc.). Also, a wait-list group would provide a control group (albeit not randomly selected). All participants who do not start in the initial group will be asked if they still want to participate in a wait-list group; if they do, we will contact them 8 weeks after their initial surveys were completed, ask them to repeat the surveys, then start them in the Pilates program.

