refer t	o activ	all the gentle exercise that you did in the last 7 days . Gentle activities ities that involve movement or body awareness, but do not make you der than normal. Think only about those physical activities that you did for ninutes at a time.
Pil	ates (i	ne last 7 days , on how many days did you do gentle physical activities like f not included under Moderate Activity, above), Tai Chi, yoga, breathing s or stretching? Do not include walking.
		_days per week
		No gentle physical activities   Skip to question 5
8.	How m	uch time did you usually spend doing gentle physical activities on one of those days?
		hours per day
		minutes per day

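### The activity measure for hypothesis 1b can include the assigned Pilates sessions, so a rise in it alone cannot show that people became more active beyond doing the course

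*Combined protocol and SAP*

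**What the plan says.** Section 3 gives hypothesis 1b as "Increased physical activity (measured using IPAQ with additional questions"). Section 2 gives the purpose: "We will also measure physical activity, to determine whether participation in Pilates allows people to become more active". It explains that questions on mind-body exercise (Pilates among them) and strengthening are added "as these activities are not included in the IPAQ".

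In Appendix G, added item 7 asks on how many of the last 7 days the respondent did gentle activity. Its examples are Pilates, if "not included under Moderate Activity, above), Tai Chi, yoga, breathing" exercises and stretching. Item 8 asks for the time spent. A note to the appendix says that the added items do not belong to the IPAQ.

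On the intervention, section 6a says: "Subjects will commit to doing 3 Pilates modules per week, for a total of 75-90 minutes/week". Wait-list participants are contacted 8 weeks after their first surveys; the team will "ask them to repeat the surveys, then start them in the Pilates program".

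Section 6e lists IPAQ, with no further definition, in the repeated-measures ANOVA (pretest, 8 weeks, 6 months) and in the ANOVA of 8-week change between groups. It plans descriptive statistics on module use, and it enters compliance in the regressions that predict BIoH after the intervention and at 6 months. Section 2 treats continued practice as a matter of its own: "We will also monitor whether subjects continue to do the Pilates exercises at 6 months, either using the videos or on their own".

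**The concern.** The 8-week comparison sets a group that has been asked to do three Pilates sessions a week against a group that has been asked to do none. If the activity score includes those sessions, it can differ between the groups even when nothing else in anyone's week has changed. The wait-list cannot remove this, because the sessions are exactly what differs. The pre-post and 6-month comparisons are affected in the same way for as long as participants keep up the Pilates.

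At stake is what a positive 1b result would mean. It could mean that Pilates helped people to do more of other things, or only that they did the course. One undivided score cannot tell these apart, and section 6e has no rule that would.

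**Working it through.** **Inputs**
- Assigned sessions: 3 per week, stated as 75-90 minutes/week (section 6a).
- Module length: 25 minutes, including some resting activities (section 6a). The modules also contain education and relaxation training (section 2).
- Pilates permitted at entry: up to 30 minutes/week (section 4b, exclusion vi).
- Recall window: the last 7 days (Appendix G). The post-test comes at the end of the 8 weeks (section 6a).
- SD of change in the IPAQ, and the unit of the score: not given.

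**The plan's own figure.** 3 × 25 = 75 minutes/week, which reproduces the lower end. The upper end needs 90 / 3 = 30 minutes per session; section 6a attributes the range to exact module length.

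**Built-in rise if the added items count**, with all other activity unchanged:
- Full compliance, no earlier Pilates: 75 to 90 minutes/week.
- Full compliance, replacing 30 minutes/week of earlier Pilates: 75 − 30 = 45 to 90 − 30 = 60.
- Half compliance, no earlier Pilates: 75 / 2 = 37.5 to 90 / 2 = 45.

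The 75-90 is a ceiling. Participants may not report education and rest as activity, and the weekly message described in section 7c allows them to do little or no Pilates.

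**Built-in rise if section 6e means the standard items only.** Let p be the share of Pilates time entered under the moderate item. The rise is p × (75 to 90):

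| p | Minutes/week |
|---|---|
| 0 | 0 |
| 0.5 | 37.5-45 |
| 1 | 75-90 |

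The documents do not give p. Item 7 shows that the form expects it to exceed zero for some respondents, although section 2 says that such activities lie outside the IPAQ.

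**Can the sessions be separated afterwards?** Only in part. Items 1-6 and 7-8 are separate questions, so their totals can be split. But item 7 pools Pilates with Tai Chi, yoga, breathing exercises and stretching, so activity without Pilates cannot be read directly off the form.

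**Chance of a significant result from the sessions alone.** This needs the missing SD. Purely to show how much depends on it, assume 225 per group (the wait-list is formed "after we have already recruited 225 subjects", and section 4e makes it equal in size), full follow-up, a two-sided 5% test and unweighted minutes. With a shift of 75, the probability is about Φ(75 / (SD × √(2/225)) − 1.96):
- assumed SD 200: 0.98
- assumed SD 600: 0.26

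That spread is too wide to support any statement of likelihood.

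**The case against.** The strongest reply has three parts.

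First, section 6e says only IPAQ, and Appendix G says that the added items are not part of it. On that reading Pilates enters only when a respondent classes it as moderate. The modules are described as gentle and mostly done lying down, and the gentle item names Pilates, so misplacement may be uncommon. The remark about moderate activity in item 7 can be read as a guard against double counting. This stands as far as it goes: on this reading the built-in rise may be zero. But hypothesis 1b names the additional questions as part of its measure, so the plan does not settle which reading applies.

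Second, Pilates is physical activity, and the questions were added in order to track it. For people with low exercise tolerance, taking it up is a real gain. This stands too: total activity is a fair reading of 1b. It does not follow that a rise in total activity answers the question in section 2 about what taking part in Pilates allows people to do.

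Third, module use is already to be described, and 1b is a non-primary outcome in a pilot that admits its evidence will not be strong. That limits the consequence. But the module-use statistics are not connected to the IPAQ comparison, and piloting the outcome tools is itself objective 2.

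A reader might go further and infer that the 1b score certainly counts the sessions, or that a significant 1b result is likely from this source alone. The documents support neither: no scoring rule is written, and no SD is given.

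**Conclusion.** The point holds in limited form. As written, 1b can rise in the Pilates group because of the assigned sessions alone. The size is at most about 75-90 minutes/week if the added items count and compliance is full, and 45-60 if earlier Pilates at the entry limit is replaced. It may be zero if only the standard items are scored and nobody enters Pilates as moderate. These figures assume that other activity does not change; they fall with lower compliance, with displacement of other activity, or if rest and education go unreported.

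A rise in total activity would be a true finding about total activity. It would not by itself show that people became more active beyond doing the course. That conclusion needs no SD. How often the sessions alone would produce a significant result cannot be known from the documents. The primary BIoH conclusion is not touched. This should be fixed because 1b is a named hypothesis and the remedy is cheap.

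**What to change.** In section 6e, state the unit of the activity score and define two scores:

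1. **Items 1-6**, the score that answers the question in section 2. Note its limits: it leaves out yoga, Tai Chi and stretching, because item 7 pools them with Pilates, and it may still hold Pilates entered as moderate.
2. **Items 1-8**, total activity including Pilates, with items 7-8 also reported separately.

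State that a rise in score 2 alone will be read as uptake of the course and not as other activity.

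Add a sensitivity analysis of score 2 minus reported Pilates minutes, floored at zero. The minutes come from Appendix C item 14 and Appendix I.2 question 4. Appendix I.2 is titled for use after 8 weeks of Pilates and at 6 months, so question 4 should also be asked at the end of the wait. Note that the subtraction over-corrects respondents who did not enter Pilates in the questionnaire, and that a typical week is not the last 7 days. Set the result beside the module-use descriptives already planned.

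Make no change of wording between a participant's baseline and follow-up, or between groups. The groups enrol in sequence, so a mid-study change would be mixed up with group.

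The cost is one extra reported score, one existing question asked at one more time point and one sensitivity analysis. Some misclassification of Pilates will remain.

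Two minor form corrections are separate from the above. In Appendix G, a respondent with no gentle activity at item 7 is sent back to item 5 (walking); the target should be item 9 (sitting), and the live survey should be checked. The strengthening question promised in section 2 is not among items 1-9; add it on the same condition of consistency across time points and groups, or remove the promise.
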